12.0 HEALTH OUTCOMES ANALYSES

Not Applicable.

13.0 **INTERIM ANALYSIS**

No interim analysis is planned for this study.

14.0 DETERMINATION OF SAMPLE SIZE

The sample size of approximately 25 randomized participants in each of the 4 treatment groups is not based on statistical power consideration due to the lack of information of AGN-241751 for the variability of change from baseline to 1 day after first dose in MADRS total score.

15.0 STATISTICAL SOFTWARE

Statistical analyses will be performed using version 9.4 or newer of SAS.

16.0 DATA HANDLING CONVENTIONS

16.1 VISIT TIME WINDOWS

Table 16-1 presents the visits assigned for efficacy and safety analyses and the corresponding range of treatment days (window) during which an actual visit may occur.

Table 16-1 Visit Time Windows

Derived Visit	Scheduled Visit Day^a	Window
Baseline	Screening/Day 1 (Visit 2)	last nonmissing assessment before Index1 ^a
Day 2	Day 2 (Visit 3)	Days (Index1 ^a +1, IndexA ^b -1)
Day 8	Day 8 (Visit 4)	IndexA ^b
Day 9	Day 9 (Visit 5)	Days (IndexA ^b +1, IndexA ^b +4)
Day 15	Day 15 (Visit 6)	Days (IndexA ^b +5, day of final double blind visit or ET Visit occurring after IndexA ^b +5)
End of Double-Blind Treatment	The last available post-baseline assessment (unscheduled assessments) during the double-blind treatment period	
Safety Follow-up (Day 22)	Days [Day after final double-blind visit or ET visit occurring after Day 15 (Visit 6)/Early Termination visit]	

a Index1: Day of first double-blind dose

b IndexA: Day of second double-blind dose, if not received, use Index1 + 7 days

If the assessment date (if the assessment date is unavailable, use visit date instead) is on or after the date of the first dose of study treatment, the study day is calculated by assessment date – date of the first dose of study treatment + 1. If the assessment date is before the date of the first dose of study treatment, the study day is calculated by assessment date – date of the first dose of study treatment. Therefore, a negative day indicates a day before the start of the study treatment.

If a participant has 2 or more visits within the same window, the last visit with a nonmissing value will be used for analysis.

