Participants will have 7 study visits during the study. The first 6 visits will occur in the following pattern: the Screening Visit (Visit 1; up to Day -14); at Visit 2 (Day 1 of the randomized inpatient treatment); at Visit 3 (1 day following the inpatient treatment day); at Visit 4 (7 days following the first inpatient treatment day, which is the second inpatient treatment day); at Visit 5 (1 day following the second inpatient treatment day); and at Visit 6 (7 days following the second inpatient treatment day). If necessary, study visits may be conducted up to 2 days before or after the scheduled visits with the exception of visits that are 1 day apart (ie, Visits 2 and 3 must be conducted 1 day apart; and Visits 4 and 5 must be conducted 1 day apart). Participants will enter a 1-week safety follow-up period and return for Visit 7. Participants who prematurely discontinue from the study before completing the double-blind treatment should enter the 1-week safety follow-up period. Additional follow-up visits may be scheduled within 30 days, if necessary for safety reasons.

Figure 4-1

Study Design Diagram

FU = follow-up; IP = investigational product.

All treatments will be presented to participants as oral once daily dosing throughout the study.

At Visit 2 (Day 1 of the randomized inpatient treatment), all participants will be randomized to receive the first treatment, followed by blinded placebo on Days 2 through 7.

Starting at Visit 4 (Day 8), participants will then start 7 consecutive days of double blinded randomized treatment, administered once daily through Day 15.

The schedule of activities for Study 3125-104-002 is presented in [Table 4-1](#). The double-blind treatment period starts with the first dose of study (Day 1) treatment and ends with the last dosing day (Day 15).

Table 4-1 Schedule of Activities (SoA)							
		Double-blind Treatment Period					Safety Follow-up Period
Visit	Screening (1)	2	3	4	5	6/ET^a	7
Study Day	up to -14 days	1	2	8	9	15	22
Informed consent	x						
Medical (surgical, neurologic) and psychiatric histories	x						
Prior medication history	x						
Inclusion/exclusion	x	x					
Randomization assessment		x					
Clinical laboratory determinations ^b	x	x				x	
Urine drug screen	x					x	
Serum pregnancy test	x					x	
Pharmacogenomics consent and sample ^c				x			
Vital signs ^d	x	x	x	x	x	x	x
ECG	x					x	
Physical examination	x					x	
SCID	x						
MADRS	x	x	x	x	x	x	x
CGI-S	x	x	x	x	x	x	
BPRS+	x		x	x	x	x	
CADSS	x		x	x	x	x	

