10.2 SECONDARY EFFICACY PARAMETER

The secondary efficacy parameter will be the change from baseline in MADRS total score at Day 8 and Day 9 after single oral dose, on Day 15 after repeated dose, and on Day 22, 7 days after the completion of AGN-241751 dosing. The primary analysis for the secondary endpoints will be performed using an MMRM with treatment group, visit, pooled study center, and treatment group-by-visit interaction as fixed effects and the baseline value and baseline value-by-visit as covariates. An unstructured covariance matrix will be used to model the covariance of within-participant scores. The Kenward-Roger approximation will be used to estimate denominator degrees of freedom ([Kenward and Roger 1997](#)). These analyses will be performed based on all postbaseline scores using only the OCs without imputation of missing values. The Day 1 predose MADRS will be used as baseline for all analysis. MADRS assessments at all study visits will be included in the MMRM model. Key secondary endpoint descriptive statistics and associated statistical testing results from the MMRM model will be presented by visit.

In addition, a sensitivity analysis using the multiple imputation (MI) approach under missing not at random (MNAR) assumptions will be performed on the primary and key secondary efficacy parameters.

For the sensitivity analysis of the primary endpoint, change from baseline in MADRS totals score at 1-day post Day 1 and secondary endpoint, change from baseline in MADRS totals score at Day 8, Day 9, Day 15, and Day 22, the following steps will be followed to generate datasets and analyze the data:

1. Generate the imputed datasets:

The implementation of the pattern-mixture model (PMM) with control-based pattern imputation of Ratitch and O'Kelly (2011) will be used to impute missing data under the MNAR assumption.

- Intermittent (non-monotone) missing data in both treatment groups are imputed using the Monte-Carlo Markov chain (MCMC) method under the MAR assumption.
- Remaining monotone missing data are imputed using a PMM approach using a sequential regression imputation model estimated based on data from the placebo arm only. 50 imputed datasets will be generated.

2. Model based key estimates LSMean difference between treatment group and standard error) will be obtained for the change from baseline in MADRS total score at day 2 (1 day after first dose), Day 8, Day 9, Day 15, and Day 22 for each imputed dataset using the same MMRM.

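### The Day 22 row of SAP Table 16-1 has no study-day limits, so it is unclear which follow-up MADRS scores count as Day 22

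*SAP*

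**What the plan says.** In SAP Table 16-1 (Section 16.1) the Day 2, Day 8 and Day 9 windows are counted in days from the first or second double-blind dose. IndexA is the "Day of second double-blind dose, if not received, use Index1 + 7 days". The Day 15 window opens at IndexA+5 and closes on the "day of final double blind visit or ET Visit occurring after" that same day. The Safety Follow-up (Day 22) row reads "Day after final double-blind visit or ET visit occurring after Day 15 (Visit 6)/Early Termination visit" and carries no day number as a limit at either end. A note under the table says: "If a participant has 2 or more visits within the same window, the last visit with a nonmissing value will be used for analysis". Nothing covers the converse case of one visit that meets two windows.

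SAP Section 10.2 makes MADRS change "on Day 22, 7 days after the completion of AGN-241751 dosing" a secondary endpoint, and the MADRS from every study visit enters the MMRM as observed cases. In the MNAR sensitivity analysis, intermittent gaps are imputed by MCMC under MAR. Only the remaining monotone gaps are imputed from a placebo-arm model.

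SAP Section 4.0 supplies the follow-up data: "Participants who prematurely discontinue from the study before completing the double-blind treatment should enter the 1-week safety follow-up period". The schedule of activities places a MADRS at Visit 6/ET and another at Visit 7. Apart from the visits that must be one day apart, "study visits may be conducted up to 2 days before or after the scheduled visits". Finally, "Additional follow-up visits may be scheduled within 30 days, if necessary for safety reasons".

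**The concern.** Day 22 is meant to show whether an effect persists a week after the repeated dosing of Days 8-15. A window tied only to the last or ET visit moves with the participant. Someone who leaves in the first or second week brings a score from well before Day 22, after incomplete dosing, and the treatment-by-visit terms of the MMRM treat it as a Day 22 score.

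Two things are at stake. First, the content of a key secondary cell depends on how a programmer reads one ambiguous row. Second, a dropout whose Day 22 cell looks filled is no longer a monotone dropout for the sensitivity analysis, so the MNAR check is weakened for the participants it is there to test.

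**Working it through.** **Inputs.** Index1 = Day 1 and IndexA = Day 8 (the planned day, and also the fallback 1 + 7 when the second dose is not received). Follow-up is taken at ET + 7, from the 1-week follow-up period. The visit tolerance is ±2 days; applying it to follow-up after an ET visit is my assumption.

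**Windows with IndexA = 8.** Day 2 is Days 2-7, Day 8 is Day 8, and Day 9 is Days 9-12. Day 15 runs from Day 13 to a final or ET visit after that point; if ET came earlier there is no valid closing day, and I take the window as empty. Day 22 is any day after the final or ET visit.

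**The plan's own figure.** For a completer, 15 + 7 = Day 22, which falls in the Day 22 window only. The row works as intended here.

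**Early terminators, reading the row as anchored to the ET visit.**

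| ET day | Follow-up (ET + 7) | Windows met |
|---|---|---|
| 3-5 | 10-12 | Day 9 and Day 22 |
| 6-7 | 13-14 | Day 22 only |
| 8-12 | 15-19 | Day 22 only |
| 13-14 | 20-21 | Day 22 only |

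The tolerance blurs the first boundary. ET on Day 6 or 7 with follow-up two days early gives Day 11 or 12, which is in both windows. ET on Day 4 or 5 with follow-up two days late gives Day 13 or 14, in Day 22 only.

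Days 13-19 are 9 to 3 days before Day 22 (22 − 13 and 22 − 19). Participants with ET on Days 6-7 had one randomized dose on Day 1 and then placebo. Those with ET on Days 8-12 had started the second-week dosing but not finished it.

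**The other reading, only ET visits after Day 15.** Follow-up on Days 13-19 then has no window, and Days 10-12 meet Day 9 alone. None of these values is Day 22.

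**Effect on the sensitivity analysis, ET-anchored reading.** Take ET on Day 6. The ET score falls in the Day 2 window, Days 8, 9 and 15 are empty, and Day 22 is filled. The three gaps are then intermittent and imputed under MAR, and Day 22 is not imputed at all. With Day 22 left empty, Days 8, 9, 15 and 22 form a monotone tail and take the placebo-based model.

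**Upper side.** Additional follow-up within 30 days could reach Day 45 if counted from Day 15 (15 + 30) or Day 52 if counted from Day 22 (22 + 30). A MADRS taken then is still in the Day 22 window, and the last-value rule would let it replace a completer's true Day 22 score.

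**Scale, by assumption only.** If 1 to 5 of 25 participants in an arm contribute such values, the share is 1/25 = 4% to 5/25 = 20%. With an assumed 5-point gap from the true Day 22 level, the raw arm mean moves by 0.04 × 5 = 0.2 to 0.20 × 5 = 1.0 point. With an assumed SD of 8 to 12, the standard error of a two-arm difference is SD × √(2/25), about 2.3 to 3.4 points.

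**The case against.** The best defence is that ET + 7 is itself about a week after dosing stopped, so anchoring to the last visit fits the endpoint's description. That covers the interval but not the exposure. SAP Section 5.0 sets Day 22 alongside Day 15 after repeated dosing, and a participant who left before Day 8 had no repeated dosing. Whether off-treatment scores belong in the analysis is an estimand question that day limits alone do not settle. Even if they do belong, a score from Day 13 is not a measurement at Day 22.

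Other parts of the defence stand. A reader might infer that every early dropout's follow-up on Days 10-14 becomes Day 22. The table does not establish that, because Days 10-12 also meet the Day 9 window. A reader might also infer that the Day 22 set is wrong however the row is read. That is not supported either: if only ET visits after Day 15 count, these scores stay out of Day 22 and the cell is left missing. The ET-anchored reading is the more natural one, because the row ends by naming the Early Termination visit, but the wording does not exclude the other.

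The assumed shift is also small next to the standard error above. It would largely cancel between arms with similar dropout and similar score gaps.

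**Conclusion.** The point holds as a specification gap. The Day 22 row has no lower or upper study-day limit and permits two different datasets for a key secondary time point. On the natural reading, follow-up from ET on Days 6-12 (Days 13-19) enters that endpoint, the Day 22 cell is not imputed, and earlier gaps move from placebo-based to MAR imputation. An additional follow-up MADRS could also displace a true Day 22 value, but only if one is taken; the schedule does not require it.

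A reader might go further and quote a bias in points. The documents do not support that. They give no dropout rate, score difference or SD, and neither the size nor the direction of bias can be derived. The day mapping rests on follow-up at ET + 7 and on treating the Day 15 window as empty when ET comes before it opens. This row does not define the Day 2 primary endpoint, and Part A is not powered, so this is a correction to make before database lock rather than a threat to the main result.

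**What to change.** Rewrite the Day 22 row of Table 16-1 with two conditions:

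- The final double-blind or ET visit falls in the Day 15 window, that is, on or after IndexA+5.
- The follow-up assessment falls within stated limits wide enough for the permitted tolerance, for example IndexA+10 to IndexA+18 (Days 18-26 with IndexA = 8). These limits come from Visit 6 at IndexA+7 ± 2 and follow-up 7 ± 2 days later: 5 + 5 = 10 and 9 + 9 = 18. A lower limit of Day 20 could drop a compliant completer seen on Day 18 or 19.

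Both conditions are needed, because ET on Days 11-12 gives follow-up on Days 18-19, inside the day limits.

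List all other follow-up MADRS values but keep them out of the MMRM. Do not remap them to Day 9 or Day 15, since that only moves the incomplete-dosing problem to another cell. Treat Day 22 as missing for these participants, so that the planned control-based imputation applies. Within the limits, stating that the scheduled Visit 7 score takes precedence would stop an unscheduled MADRS from replacing it.

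The cost is one table row and a sentence or two of text, no change to trial conduct, and slightly fewer observed Day 22 values.

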9.1.2. The Montgomery-Åsberg Depression Rating Scale

The MADRS ([Montgomery and Åsberg 1979](#)) is a clinician-rated scale ([Appendix 8](#)). The MADRS will be used to assess depressive symptomatology. Participants are rated on 10 items to assess feelings of sadness, lassitude, pessimism, inner tension, suicidality, reduced sleep or appetite, difficulty concentrating, and lack of interest. Each item will be scored on a 7-point scale. A score of 0 indicates the absence of symptoms, and a score of 6 indicates symptoms of maximum severity.

A qualified rater (ie, who meets the training requirements and qualifications set by the rater training vendor) at each investigational center will conduct the MADRS assessment.

For Part A, at Screening (Visit 1) and Visit 2 (predose), the MADRS will be administered with a look-back timeframe of 1 week. At all other evaluations, the MADRS will be administered with a look-back timeframe of “since last evaluation.”

For Part B, at Visit 1 (Screening) and Visit 2 (Day –1, baseline), the MADRS will be administered with a look-back timeframe of 1 week. At all other evaluations, the MADRS will be administered with a look-back timeframe of “since last evaluation.”

MADRS assessments will be performed as specified in the schedule of activities in Section [2.1](#) (Part A) and Section [2.2](#) (Part B).

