C-SSRS	x	x	x	x	x	x	x
	Double-blind Treatment Period						Safety Follow-up Period
Visit	Screening (1)	2	3	4	5	6/ET ^a	7
Study Day	up to -14 days	1	2	8	9	15	22
HAM-A ^c		x	x	x		x	
AEs		x	x	x	x	x	x
Concomitant medications	x	x	x	x	x	x	x
Study treatment administration in the clinic		x		x			
Study treatment compliance		x		x	x	x	

Screening procedures may be conducted on up to 2 separate dates where necessary to accommodate participant and site schedule; however, every effort should be made to conduct all procedures as early as possible in the screening period.

If necessary, study visits may be conducted up to 2 days before or after the scheduled visits except for visits that are 1 day apart (ie, Visits 2 and 3 must be conducted 1 day apart, and Visits 4 and 5 must be conducted 1 day apart).

^a Performed for all participants, including those prematurely discontinued after randomization. Clinically significant findings upon termination should be followed until the condition returns to prestudy status or can be explained as unrelated to study treatment. If necessary, additional follow-up visits can be scheduled.

^b Participants will be requested to fast overnight or for at least 8 hours before arriving at the study center for appointments involving the collection of clinical laboratory blood tests. Clinical laboratory tests can be done at any visit for safety reasons at the discretion of the investigator.

^c A separate ICF must be signed before the pharmacogenomic blood sample is taken. Participation is optional. This ICF may be signed at any visit during the study; however, the sample should be collected at any visit after the participant has been randomized.

^d Height will only be measured at Visit 1 (Screening); pulse rate, blood pressure, temperature, and body weight will be assessed at every visit. Blood pressure and pulse will be assessed while the participant is supine and standing.

^e HAM-A will be assessed predose at Visits 2, 3, 4, and 6/ET. The HAM-A will be collected only from participants entering the study after the amendment has been IRB approved.

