10.1 PRIMARY EFFICACY PARAMETER

The primary efficacy parameter will be the change from baseline in MADRS total score at 1 day after first dose and will be analyzed using a mixed-effects model for repeated measures (MMRM) model with treatment group, visit, pooled study center, and treatment group-by-visit interaction as fixed effects and the baseline value and baseline value-by-visit as covariates. An unstructured covariance matrix will be used to model the covariance of within-participant scores. If the model fails to converge based on the unstructured covariance matrix, then structures of Heterogenous Toeplitz, Toeplitz, and Compound Symmetry will be applied, in the specified order, until the model converges. The Kenward-Roger approximation will be used to estimate denominator degrees of freedom ([Kenward and Roger 1997](#)). These analyses will be performed based on all postbaseline scores using only the observed cases (OC) without imputation of missing values. MADRS assessments at all study visits will be included in the MMRM model. Primary endpoint descriptive statistics and associated statistical testing results from the MMRM model will be presented.

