10.3 ADDITIONAL EFFICACY PARAMETERS

Additional efficacy parameters are as follows:

- Change from baseline in Clinical Global Impressions-Severity (CGI-S) at Day 2 (1 day after first dose), Day 8, Day 9 and Day 15
- MADRS responder status at Day 2 (1 day after first dose), Day 8, Day 9, Day 15 and Day 22
- CGI-S responder status at Day 2 (1 day after first dose), Day 8, Day 9 and Day 15
- MADRS remitter status at Day 2 (1 day after first dose), Day 8, Day 9, Day 15 and Day 22
- Time to first response
- Time to first remission

Analysis of change from baseline in CGI-S score will be performed using a similar MMRM to that used for the key secondary parameter. Multiple comparison procedure will not be applied to the above additional efficacy parameters.

Plots of fitted (least squares) mean values and their standard errors based on the MMRM model for the change from baseline in MADRS total score and in CGI-S score, respectively, will be presented by treatment group and by visit.

CGI-S responder is defined as participants achieving a score of ≤ 2 on the CGI-S of Illness scale.

During the randomized treatment period, 2 types of events for MADRS total score will be defined based on the following criteria:

- Responder: $\geq 50\%$ reduction from baseline MADRS total score
- Remitter: MADRS total score ≤ 10

Rates of responders and remitters will be reported by treatment group for each timepoint (Days 2, 8, 9, 15, and 22 after first dose of randomized treatment). A logistic regression model with LOCF imputation will be used to model the probability of a response or the probability of a remission as a function of a treatment group and baseline MADRS or CGI-S total score. The LOCF approach will be used to impute missing postbaseline values, provided that at least 1 postbaseline assessment is available. Missing values between the baseline and the first nonmissing postbaseline will be imputed with the baseline value. If all the postbaseline values are missing, the baseline value will not be carried forward. Only the total score of a parameter will be imputed using the LOCF approach; individual item scores will not be carried forward. Bar charts for the rates of responders and remitters in MADRS total score will be presented by treatment group and by study day.

Descriptive statistics for the first three additional endpoints and their associated statistical testing results from the MMRM models and logistic regression will be respectively presented by visit.

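### SAP Table 16-1 lets an early-termination or unscheduled MADRS taken before the second dose replace an observed Visit 3 score in the primary Day 2 analysis

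*SAP*

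**What the plan says.** SAP 10.1 fixes the endpoint by time: "The primary efficacy parameter will be the change from baseline in MADRS total score at 1 day after first dose". The visit schedule protects that timing. SAP 4.0 allows most visits to move by 2 days but makes an exception: "Visits 2 and 3 must be conducted 1 day apart".

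SAP 16.1 decides which score is analysed under each visit label, for efficacy as well as safety. In Table 16-1, derived Day 2 (Visit 3) runs from Index1+1 to IndexA−1, where Index1 is the day of the first double-blind dose. Footnote b defines the other anchor: "IndexA: Day of second double-blind dose, if not received, use Index1 + 7 days". Derived Day 9 (Visit 5) runs from IndexA+1 to IndexA+4. For several visits in one window the rule is: "If a participant has 2 or more visits within the same window, the last visit with a nonmissing value will be used for analysis".

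The MADRS is marked at Visit 6/ET in SAP Table 4-1, and footnote a says of that visit: "Performed for all participants, including those prematurely discontinued after randomization". Protocol 8.1 also asks for an ET visit after premature discontinuation, whatever the cause. On the model input, SAP 10.1 says only this: "MADRS assessments at all study visits will be included in the MMRM model".

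**The concern.** The Day 2 window is up to several days wide, while the endpoint it feeds is a 1-day change. A wide window does no harm if the on-time score has priority, but the tie rule gives priority to the latest score. Someone who gave a valid Visit 3 score and left a few days later is therefore analysed on a score from the Days 2–7 placebo-tablet period.

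The replacing score also rates a different interval. Protocol 9.1.2 sets a one-week look-back at Screening and Visit 2, then says: "At all other evaluations, the MADRS will be administered with a look-back timeframe of" the time since the preceding evaluation. An ET MADRS after Visit 3 therefore does not cover the first day after the dose.

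Replacement need not be random. Protocol 7.8 allows participants whose symptoms worsen or are not adequately controlled to leave, and Protocol 8.1 requires withdrawal on suicide-related criteria. Early ET scores may differ systematically from Visit 3 scores; whether they differ by arm is unknown. The primary Day 2 contrast, the Day 2 responder and remitter rates, and the Day 9 key secondary timepoint all use the value selected in this way.

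**Working it through.** The documents give no power, SD, effect size or dropout rate, so there is no planned figure to reproduce. The check applies the Table 16-1 rule to possible visit patterns and then sizes the effect under stated assumptions.

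**Step 1: the windows.** Take Index1 = Day 1 and read the bounds as inclusive; exclusive bounds would leave out Day 2 itself. The Days 2–7 tablets are single-blind placebo, so they do not count as the second double-blind dose.

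- Second dose not received: IndexA = 1 + 7 = Day 8. The Day 2 window is Days 2–7 and the Day 9 window is Days 9–12.
- Second dose at Visit 4 on Day 6, 7, 8, 9 or 10 (Day 8 ± 2): the Day 2 window ends on Day 5, 6, 7, 8 or 9. The Day 9 window is Days 7–10, 8–11, 9–12, 10–13 or 11–14.

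**Step 2: the tie rule.** Take a Visit 3 score on Day 2, no second dose, and an ET MADRS on a later day.

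| Day of ET | Derived visit of the ET score | Score analysed as Day 2 |
|---|---|---|
| 3, 4, 5, 6 or 7 | Day 2 | ET score (2–6 days after the first dose); Visit 3 dropped |
| 8 | Day 8 | Visit 3 score |
| 9 | Day 9 | Visit 3 score |

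The Day 15 row accepts an ET visit only late in the second period, so among the double-blind visit rows an ET on Days 3–7 maps only to Day 2. For Visit 5 the same happens when a later MADRS falls on IndexA+2 to IndexA+4.

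**Step 3: is there an exemption?** SAP 10.1 and 10.2 give no priority to Visit 3 or Visit 5. SAP 16.3 covers repeated and unscheduled assessments, but only of safety parameters. The End of Double-Blind Treatment row already holds the last score, so overwriting Day 2 is not needed to preserve it.

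**Step 4: size (assumed inputs).** Let d be the number of replaced scores in an arm of 25, and D the difference between the later score and the Visit 3 score, assumed to be 5–10 points.

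- Shift in one arm's raw mean = d × D / 25. For d = 1: 5/25 to 10/25 = 0.2–0.4. For d = 2: 0.4–0.8. For d = 3: 0.6–1.2.
- Shift in the active–placebo contrast = (dA × DA − dP × DP) / 25. With equal D: (1,1) gives 0; (2,1) gives 0.2–0.4; (3,1) gives 0.4–0.8.
- SE of a 25 versus 25 difference = SD × √(2/25): 8 × 0.283 = 2.26 and 10 × 0.283 = 2.83 (SD assumed).
- Contrast shift relative to SE: 0.2/2.83 = 0.07 up to 0.8/2.26 = 0.35.
- One participant whose Day 2 responder status changes moves that arm's rate by 1/25 = 4 percentage points.

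**The case against.** The strongest reply is that the reach is narrow. Visit 4 falls on IndexA itself, and Visit 6 can come no earlier than IndexA+5 (7 days after the second inpatient day, less 2), which is where the Day 15 window opens. On-schedule visits therefore never displace Visit 3 or Visit 5. By the planned route, the primary endpoint is touched only when someone attends Visit 3 and has an ET MADRS on Days 3–7. That is right, and it limits the size of the problem. It does not change what the rule does to those participants.

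The unscheduled route is weaker, since no unscheduled MADRS is planned. The moving end of the Day 2 window matters only there, because a participant whose ET precedes the second dose always has IndexA on Day 8. Still, Table 16-1 itself provides for unscheduled assessments, and the tie rule covers any visit in the window.

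It is also fair that the illustrated contrast range is not a bound. The zero for equal numbers needs equal D in both arms. Three replacements in one arm and none in the other would give 0.6–1.2 points, or 0.21–0.53 SE (0.6/2.83 to 1.2/2.26). Part A is a proof-of-concept study not sized on power, and nothing here shows that a conclusion would change.

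Finally, keeping Visit 3 at Day 2 removes a discontinuer's last score from the by-visit MMRM and from the imputation that feeds it. That is a real but small loss. The present rule also discards one of the two scores, and it discards the on-schedule one.

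**Conclusion.** The point holds. As written, Table 16-1 and its tie rule replace an observed 1-day score with a later one whenever a later MADRS falls in the Day 2 window, which contradicts the primary parameter in SAP 10.1. The reading of the rule rests only on the SAP text and on inclusive window bounds. Participants with no later MADRS in the window are unaffected.

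The effect on results cannot be computed from the documents. Under the assumptions shown it is a fraction of one standard error, and it biases the contrast only so far as replacements differ between arms in number or size. This is a defect to correct before database lock, not a threat to the trial.

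**What to change.** In SAP 16.1, for derived Day 2 and Day 9, replace the last-visit rule with: *use the scheduled visit (Visit 3 or Visit 5) if its value is nonmissing; otherwise use the assessment closest to the target day (Index1+1 or IndexA+1), taking the earlier on ties.* Flag fallback records as off target. A participant who missed Visit 3 then still has a Day 2 record, and no later score overwrites an observed one.

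State that a later ET score is kept for the End of Double-Blind Treatment record and as the last observed value for the responder and remitter analyses. There SAP 10.3 provides: "The LOCF approach will be used to impute missing postbaseline values, provided that at least 1 postbaseline assessment is available". Values carried forward to later visits then stay as they are now.

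In SAP 10.1 and 10.2, align the sentence on MMRM input, for example: *one record per derived visit, selected by the Table 16-1 rules, enters the model.*

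One existing overlap can be settled in the same edit. After an ET on Days 3–7, the follow-up MADRS can fall on Days 9–12 and so fit both the Day 9 and Safety Follow-up rows. The table should say which row takes it.

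The cost is SAP wording and minor programming: the selection rule, plus the handling of the ET score for LOCF. No data collection changes.
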